1.0 PURPOSE

1.1 Name and Intended Use

The device used in this study is called the TempSure device. The study will be using the Mini Envi handpiece and may also use the Envi handpieces and Icon device (Max series).

The intended use of the TempSure device used in this study to assess the efficacy of the handpiece for the treatment of facial wrinkles. If the Icon device is used, the intended use will be for the treatment of benign pigmented and/or vascular lesions.

1.2 Objectives

1. Primary Objective:
 - Photographic evaluation with correct identification of pre-treatment 2D images when compared to the 12 week follow up images performed by three independent reviewers.
2. Assessments:
 - Photographic evaluation with correct identification of pre-treatment 2D images when compared to the 4 week follow up images performed by three independent reviewers.
 - Photographic evaluation with Fitzpatrick Wrinkle Severity Scale (FWSS) grading comparing pre-treatment images to the 4 and 12 week follow up images performed by three independent reviewers.
 - Principle Investigator assessment using the Global Aesthetic Improvement Scale (GAIS) at the 4 and 12 week follow up visit.
 - Subject assessment using the Global Aesthetic Improvement Scale (SGAIS) at the 4 and 12 week follow up visit.
 - Subject Questionnaires
 - Pre-Treatment 1
 - Post Treatment 1
 - Follow Up
3. Safety Objectives:
 - Collection of Adverse Events
 - Collection of Treatment Discomfort/Pain Evaluation

1.3 Duration of the Investigation

The sponsor anticipates that all subjects can be enrolled within 3 months. If subject participates in all required visits, then the subject's participation in this study may last up to 6 months. It is anticipated that it will take approximately 3 months to analyze the data collected during this study. The total duration of this study is anticipated to last approximately 12 months.

2.0 PROTOCOL

2.1 Protocol Methodology and Analysis

Methodology:

Subjects are to be enrolled in this clinical study if they are a healthy male or female 18 years of age or older. Up to 50 subjects will be enrolled at 3 study centers. Subjects will be enrolled into 2

groups, Group A for TempSure treatments only and Group B for TempSure and Icon treatments. Randomization will not be required as subjects will only be enrolled in Group B and treated with the Icon device if they present with pigment and/r vascular lesions. Subjects will attend a screening/pre-treatment visit which may be performed on the same day as the treatment visit. Subjects in Group A will receive up to 4 treatments with the TempSure device on the face. Subjects in Group B will receive 2 treatments with just the TempSure device and 2 treatments with both the TempSure and Icon device. Some subjects may be asked to return for an optional 5th treatment (2 – 3 weeks post last treatment) with the Icon device (and/or TempSure device) after the completion of their 4 treatments at the discretion of the Investigator. Subjects may receive a phone call 1 week (1-7 days) after each treatment to record side effects. Subjects will return for follow up visits at 4 and 12 weeks post last treatment for efficacy and side effects assessments. An unscheduled visit or phone call may be performed at any time during the study at the request of the subject or as deemed necessary by the site Investigator.

Analysis:

Upcoming generations are proving to have an interest in non-ablative aesthetic treatments and will drive demand for innovated products, procedures, and practice design.¹ Due to this shift in patient base, practices need to evolve to adapt to the newer generational ideologies. There have been rapid advances in RF technology over the past few years and the nonsurgical treatment using this energy source offers great promise to our aging population.² Radiofrequency technology for the treatment facial wrinkles and skin laxity needs to be further investigated to optimize treatment parameters for safe and effective non-ablative aesthetic treatments.

Relevance:

Over time, skin structure degrades due to a variety of internal and external conditions. As enzymes break down collagen and elastin, skin loses its suppleness and becomes loose. UV exposure, diet, and smoking among other behaviors all contribute to the skin becoming lax. Body wrinkles, particularly on the abdomen, are a sign of aging and are also a prevalent concern with postpartum women or subjects who have lost weight. It is estimated that adult skin loses approximately 1% of its dermal collagen content on an annual basis due to increased collagen degradation and decreased collagen synthesis.² Radiofrequency, ultrasound, non-ablative fractional technology, and ablative technology have all been used to varying degrees of success. The limitations of current products on the market include different side effect profiles and modes of administration.

Testability:

The TempSure device is currently cleared for use for non-ablative treatment of mild to moderate facial wrinkles and rhytids (K171262). The Icon device is currently cleared for used for the Max Series Intense Pulsed Light Handpieces for the treatment of benign pigmented epidermal and cutaneous lesions, including warts, scars and striae; removal of unwanted hair from skin types I-VI, and to effect stable long-term, or permanent, hair reduction; treatment of benign pigmented lesions, including lentigines, nevi, melasma, and cafe-au-lait; and treatment of vascular lesions, including port wine stains, hemangiomas, angiomas, telangiectasias, rosacea, facial and leg veins (K103664). This study will utilize the collection of data and imaging to support current and additional marketing claims.

Compatibility:

In earlier stages of facial wrinkles and skin laxity, and therefore younger subjects, there is normally minimal appearance of those conditions, allowing for less aggressive and therefore safer overall treatments. Younger subject's bodies are also capable of responding to the treatment quicker due to their ability to produce more collagen quicker than an older subject. As a subject gets older their condition becoming more severe, this may result in the subject needing more overall treatment and more aggressive treatments to get their body to respond the same way that a younger subject may be able to respond.

Predictive power:

While this study will observe the efficacy of the device on the face, this treatment could potentially be applied to a variety of body areas and other potential applications. Assuming there an acceptable safety profile, it would be appropriate to expect results in different areas.

2.2 Protocol Study Design

This is a prospective, open label, multi-center clinical study to collect efficacy data on the TempSure device and may also collect data on the Icon device.

2.3 Subject Selection Criteria

Subjects will meet the criteria described below:

Inclusion Criteria:

- A healthy male or female 18 years of age or older.
- Agrees to be treated with the TempSure device.
- Understands and accepts obligation not to receive any other procedures on the treatment area through the length of the study.
- Understands and accepts the obligation and is logistically able to be present for all visits.
- Is willing to comply with all requirements of the study and sign the informed consent document.

Exclusion Criteria:

- Is pregnant or of childbearing potential and not using medically effective birth control, or has been pregnant in the last 3 months, currently breast feeding or planning a pregnancy during the study.
- The subject has a cut, wound, or infected skin on the area to be treated.
- The subject is on local, oral, or systemic anesthetic agents.
- The subject has nerve insensitivity to heat in the treatment area.
- The subject has any condition or is in a situation which in the investigators opinion may put the subject at significant risk, may confound study results or may interfere significantly with the subject's participation.

Cautionary Criteria:

- The subject is currently enrolled in an investigational drug or device trial, or has received an investigational drug or been treated with an investigational device within in the area to be treated 6 months (or at the discretion of the Investigator) prior to entering this study.

- The subject has any embedded electronic device that gives or receives a signal, the device should be turned off or removed prior to treatment.
- The subject has an embedded pacemaker or implantable cardioverter defibrillator (ICD), the client’s cardiologist must be consulted prior to treatment.
NOTE: This device has not been tested on patients implanted with electronic devices that receive or emit signals, such as: Pacemakers, Implantable Cardiac Defibrillators (ICD), or Cardiac Resynchronization Therapy (CRT) devices.
- If the neutral pad would need to be placed on a subject that has a metal plate, rod, or any metal implant that could conduct heat from the Smart Handpiece or surgical handpiece.
- The subject is allergic to adhesives, such as glues on medical tape, they should be alerted that a rash may occur on the neutral pad site and an over the counter solution may be used to treat the area.
- The subject is allergic to gold, such as the metallic covering of the TempSure handpieces.
- The subject is allergic to corn, such as the corn derivative ingredient in Parker Aquasonic Gel.
- If the subject has an unhealthy expectation of the results – this is not plastic surgery and all subject should be fully informed of the treatment’s expected results.
- The subject has severe laxity or sagging that causes redundant folds of tissue or hanging skin in the area to be treated – this treatment will be ineffective.
- The subject has used Accutane (Isotretinoin) six to twelve months prior to treatment, as this can thin the skin and make it brittle.
- Studies of the use of the RF generator on subjects that have any of the following conditions is unknown:
 - Autoimmune Disease
 - Diabetic
 - Herpes Simplex
- Use caution when treating areas that have scars, tattoos, permanent makeup, and permanent brows.

Exclusion Criteria for Icon Treatments Only:

- The subject is using systemic steroids (e.g. prednisone, dexamethasone) prior to or during the course of treatment.
- The subject has a medical condition or is receiving treatment that significantly compromise healing response.
- The subject has a history of light-induced seizures.
- The subject has a history of skin photosensitivity disorders.
- The subject has a history of hypertrophic scars or keloid formation.
- The subject has a history of radiation therapy in area to be treated.

Additional Cautionary Criteria for Icon Treatments Only:

- The subject is not allergic to medications, latex or other substances that may be used during treatment course.
- The subject’s skin type is appropriate for the handpiece to be used.
- The subject is taking photosensitizing medication. Perform test spots 24 hours up to one week before considering treatment.

- The subject is currently taking blood thinning medications or anti-coagulants. The subject should discontinue the use of these medications if determined to be safe to do so by their prescribing physician. With the prescribing physician's approval, the subject should stop taking the medication at least 2 weeks prior to and throughout the treatment course.
- The subject has a condition or is taking medications that alters the ability of the blood to coagulate.
- The subject is currently using Tretinoin and topical retinoids, e.g., Retin-A®, Renova® and exfoliating products. Although use in the area to be treated is not absolutely contraindicated, it is known to make skin more sensitive and prone to exfoliation. Candidates for Icon™ treatment should be advised to discontinue the use of exfoliating creams and other exfoliating products two (2) weeks prior to and during the entire treatment course.
- The subject has a history of heat urticaria. They may develop hives with exposure to light pulses.
- The subject has Herpes I or II within the treatment area. Before a treatment, candidates should consult their primary care physician for medical evaluation and possible prophylaxis to minimize the chance of a herpetic breakout. A small percentage of persons may experience an activation of oral herpes simplex virus infection within 5-10 days after the procedure, even with appropriate prophylaxis.
- The subject has received Botulinum treatments in the treatment area. There is the possibility for increased diffusion of Botulinum, such as Botox®, as a result of edema associated with facial light-based treatment, which may result in facial asymmetry when these procedures are performed at the same visit. Many physicians recommend waiting for a minimum of 2 weeks after a Botox injection before performing facial light-based treatments. Cynosure has conducted no clinical trials and cannot recommend any specific waiting time.
- The subject has Pigmented Lesions in treatment area. If treating over a pigmented lesion, the lesion must be diagnosed as benign by a qualified practitioner prior to treatment. Inaccurate diagnosis and inadvertent treatment of a skin cancer may lead to a delay in the person receiving proper medical care.
- The subject has Cosmetic Dermal Fillers/Implants in treatment area. This Handpiece has not been evaluated or tested on areas with cosmetic dermal fillers, neurotoxins, or implants.
- The subject has had unprotected sun exposure or use of tanning beds or creams in areas to be treated. Protected sun exposure means wearing protective clothing and the daily use of a SPF-45 or greater sunscreen. Those being treated should be advised to discontinue indoor and outdoor tanning at least four (4) weeks prior to treatment, during the treatment course, and four to six (4 to 6) weeks after treatment. This will reduce the chance of skin color changes and manifestation of new pigmented lesions.
- The subject has a history of Menstrual dysfunction/Polycystic Ovarian Syndrome (PCOS). Those with menstrual dysfunction, such as PCOS and/or ovarian hyperandrogenism, may have unpredictable results. These subjects tend to have hirsutism secondary to their disease and should consult a primary care physician before a light-based treatment.
- The subject has a history of vitiligo, eczema, psoriasis, allergic dermatitis, any diseases affecting collagen including Ehlers-Danlos syndrome, and scleroderma may affect response to treatment.

- The subject is of Middle Eastern and Mediterranean descent. They may have an ill-defined hair line with no obvious transition of the hairline to the face which may put them at risk of paradoxical hair growth. These clients are at a high risk for hair stimulation and should be advised of this phenomenon before treating.

Be sure to list all concomitant medications taken or procedures performed before, during and after the trial

Subjects will be recruited for the study through the existing patient database and may also be recruited through advertisements.

Subject populations will not be eligible to participate in the study if they are vulnerable populations such as children, pregnant women, prisoners, institutionalized individuals, and any persons requiring a legally authorized representative as part of the consenting process.

Subject population characteristics that will not be eligible to participate in participate in the study include non-English speaking individuals and people who cannot read or comprehend English. Employees of the Investigator will be participating in the study.

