2.7 Treatment Procedures

- Prior to treatment 1 only, subjects will be asked to complete a Pre-Treatment 1 Questionnaire.
- The defined study area will be identified and may be marked with a surgical marker.
- Procedures for the TempSure treatment:
 - A neutral pad will be placed on the back in an area determined by the Investigator to maintain standard energy settings and to require less power from the device during the treatment.
 - The subject may be required to wear eye shields at the discretion of the Investigator.
 - Gel will be applied to the treatment area.
 - The handpiece will be placed in contact with the skin.
 - The entire defined treatment area will then be treated by delivering energy to the skin.
 - Temperature will be continuously monitored and recorded during treatment.
- Procedures for the Icon treatment:
 - All operators and subjects will wear appropriate protective eyeglasses during the pulse-light treatments.
 - The Skintel Melanin Reader may be used for objective measurement of the melanin content of skin. The Skintel Reader may provide guidance to help select test spot settings.
 - Test spots will be performed prior to treatment in an area in or close to the treatment area in order to determine safe parameters for treatment.
 - The handpiece will be placed in contact with the skin.
 - The entire defined treatment area will then be treated by delivering adjacent pulses with minimal overlap of 20% or less.

- An air-cooling system may be used during treatment. The air-cooling system allows for the continuous flow of cold air on the treatment area to ease the sensation from the pulse.
- Parameters may be adjusted throughout the treatment to increase subject comfort.
- Subjects will be asked to report the general level of treatment discomfort/pain on a scale of 0 (none) to 10 (maximum intolerable pain).
- Photographs may be taken during treatment.
- The additional treatments will follow the same procedure.
- Subjects will receive up to 4 treatments on the face. Subjects in group B may be asked to return for an optional 5th treatment with the Icon device (and/or TempSure device) at the discretion of the Investigator.

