Mild heat or hot spots may be felt during treatment by the subject. If the subject reports heat at the pad site, evaluate the site, check for epidermal injury. Skins burns may occur if subject does not report if the pad becomes too hot.

Adverse Events Pertaining to Cooling:

Anticipated transient side effects associated with forced air/contact cooling may include tingling, itching, decreased sensation, numbness, redness and pain.

Adverse Events Pertaining to the Surgical Marker:

Using surgical marker has minimal risks and may produce effects on the body such as redness or a rash. Markings may remain visible for a few days or may be removed with alcohol.

Other Cautions:

Incomplete response or no response may occur since some subjects may not respond to treatment.

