Changes to the TempSure® device are anticipated during the investigation as the Mini Envi handpiece is expected to receive clearance for use from the FDA.

The TempSure® Device Specifications are:

Surgical Connector	1 surgical monopolar port
Neutral Connector	One universal neutral connector compatible with Cynosure neutral electrodes
Smart Handpiece Connectors	One 4-pin circular connector for both RF energy delivery and temperature sensing (monopolar)
Modes of Operation	Select the Smart Handpiece or Surgical mode of operation
Maximum Power	
Temperature-Sensing Handpieces
 
 ⚠ 10mm, 15mm, and 20mm handpieces have a maximum GUI setting of 70, which provides output power of 120 Watts (+/- 20%). ⚠ 18mm handpiece has a maximum GUI setting of 25, which provides output power of 25 Watts (+/-20%). ⚠ 25mm and 30mm handpieces have a maximum GUI setting of 80, which provides output power of 165Watts (+/- 20%). ⚠ 60mm handpieces have a maximum GUI setting of 100, which provides output power of 300 Watts (+/- 20%). ⚠ FlexSure applicators are controlled by setting the temperature. During treatment, power can reach a maximum output of 300 Watts (+/- 20%). 
Ensuring that the neutral pad recommended for use with the 60mm handpiece and flexible applicator has sufficient current carrying capacity so as to assure that there is no unacceptable temperature rise under the pad is an essential performance of the TempSure platform.

The TempSure® consumables are: Handpieces, NEM Pads

The Icon device used in this study is currently cleared by the U.S. Food and Drug Administration (the FDA). The Icon device received 510(k) clearance under K103664 on March 17, 2011 for:

The Max Series Intense Pulsed Light Handpieces are intended for the treatment of inflammatory acne (acne vulgaris) and for the treatment of benign pigmented epidermal and cutaneous lesions, including warts, scars and striae; removal of unwanted hair from skin types 1-VI, and to effect stable long-term, or permanent, hair reduction; treatment of benign pigmented lesions, including lentigines, nevi, melasma, and cafe-au-lait; and treatment of vascular lesions, including port wine stains, hemangiomas, angiomas, telangiectasias, rosacea, facial and leg veins.

The Icon Device Specifications for the Max G handpiece are:

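### The heat-insensitivity exclusion covers the facial treatment area but not the neutral pad site on the back, where the protocol relies on the subject to feel and report heat

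*Combined protocol and SAP*

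**What the plan says.** Section 2.3 (Exclusion Criteria) lists: "The subject has nerve insensitivity to heat in the treatment area". Section 2.7 fixes where treatment is given: "Subjects will receive up to 4 treatments on the face". The same section places the return electrode elsewhere: "A neutral pad will be placed on the back in an area determined by the Investigator".

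The neutral pad part of section 2.14 makes three statements about that second site:

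- Heating there is expected: "Mild heat or hot spots may be felt during treatment by the subject".
- The response follows a complaint: "If the subject reports heat at the pad site, evaluate the site, check for epidermal injury".
- The consequence of silence is named: "Skins burns may occur if subject does not report if the pad becomes too hot".

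Section 2.8 requires adverse events to be documented after treatment. It does not mention looking at the pad site.

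**The concern.** The protocol names a burn hazard at the back and describes the subject's own report of heat as what stands between a hot pad and an injury. The one criterion that screens for ability to feel heat is confined to a different part of the body. In a person who feels heat normally on the face but poorly on the back, the same deficit weakens both the warning during treatment and the stated prompt to examine the skin.

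Two things are at stake. The first is subject safety at a site whose risk the protocol acknowledges. The second is ascertainment: collection of adverse events is a safety objective (section 1.2) and is summarised by group (section 2.15.6), and an event that nobody is asked to look for may not reach that summary. The primary photographic endpoint is not affected.

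**Working it through.** No formula applies and the plan gives no figure to reproduce. The check is whether any provision, read with the others, extends heat-sensation screening or a routine look to the pad site.

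**1. Does the treatment area include the pad site?** No. Section 2.7 applies gel to the treatment area, puts the handpiece on the skin and treats the whole defined area; placing the pad on the back is a separate step. Section 2.3 also names the pad when it means the pad: the cautions on metal implants and on adhesive allergy both do so. The heat-insensitivity exclusion does not.

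**2. Does another criterion reach reduced sensation on the back?**

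| Provision | Section | Reach |
|---|---|---|
| Anesthetic agents excluded | 2.3 | Any body site, but only loss of sensation caused by a drug |
| Subject must be healthy | 2.3 | General; no mention of sensation |
| Condition the investigator judges a significant risk | 2.3 | Could cover it; discretionary and does not mention the pad |
| Metal implant where the pad would go | 2.3 | Caution only; concerns conduction of heat, not sensation |

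No specific criterion covers it. The general and discretionary ones can.

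**3. Is pad temperature measured?** Section 2.7 says "Temperature will be continuously monitored and recorded during treatment" but does not say where. The temperature sensing described in section 4.0 belongs to the Smart Handpiece connector, and no pad sensor is described. Section 4.0 also requires enough current capacity in the neutral pad to prevent an unacceptable temperature rise beneath it, but ties this to the 60mm handpiece and the flexible applicator. Section 1.1 names the Mini Envi and Envi handpieces for this study.

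**4. Is the pad site looked at without a complaint?** None of the following specifies it:

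- Section 2.8 asks for adverse event documentation after treatment in general terms.
- Section 2.12 schedules an adverse event assessment at each visit, again without naming the pad site.
- Section 13.0 limits study photographs to the treatment area.
- The call after each treatment is optional (sections 2.9 and 2.12).

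**Result.** For a subject with reduced heat sensation on the back, the protocol text contains no specific exclusion and no pad-site check that is independent of the subject's report. General provisions give partial cover on both counts.

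**The case against.** The strongest reply is that the protocol does not leave such a subject unprotected.

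- **Eligibility.** A known insensate back falls naturally under the investigator's-opinion exclusion, especially since section 2.14 itself warns of pad burns when heat goes unreported. The anesthetic exclusion applies at any site. The investigator chooses where on the back the pad goes, partly so that the device needs less power, and section 3.2 treats operator experience as the main control on risk.
- **Detection.** Adverse events are documented after every treatment and assessed at every visit. Sessions are 1 to 2 weeks apart and the back must be accessible for the pad (section 2.6), so staff return to that region. The instruction to examine the site after a complaint describes a response; it does not confine adverse event recording to complaints.
- **Unseen documents.** Section 6.0 places directions for use in the Operator's Manual and says labeling will cover contraindications and hazards. Pad precautions may be there or in the Clinical Reference Guide.

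Much of this stands. A reader might infer that the subject's report is the only protection against a pad burn, or that a person with an insensate back would meet all the criteria. The text supports neither, for the reasons just given. Nor does it support saying that a burn would be absent from the adverse event count: it could be seen when events are documented. A reader might also point to diabetes as the likely route to the problem. Section 2.3 says only that use of the RF generator in diabetics is unstudied; it says nothing about sensation, so that link would have to come from outside the documents.

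What the reply does not do is close the gap. The general provisions prompt no question about the back, while the specific criterion points to another site. A burn may be noticed, but the protocol does not ask anyone to look unless heat is reported. It is also fair to say that sections 2.3 and 2.14 do not contradict each other outright: the fault is one of scope.

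**Conclusion.** The point holds in a limited form. The exclusion for heat insensitivity has a narrower scope than the hazard that section 2.14 describes, and no check of the pad site independent of the subject's report is specified. A pad burn in a subject with reduced sensation on the back could be missed, although the general adverse event documentation after treatment might find it.

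The size cannot be given as a number. The documents state no frequency of reduced heat sensation on the back and none for pad burns; the number affected is unknown and probably small. A reader might multiply up to 50 subjects by 4 sessions and quote 200. That is a ceiling on pad uses before any optional fifth session and says nothing about how many subjects are at risk, so it should not be used as a measure of the problem.

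The conclusion assumes that the treatment area means the face, as sections 2.1 and 2.7 indicate, and that the protocol text governs eligibility. If the Operator Manual or Clinical Reference Guide already contains pad-site precautions that sites must follow, the remaining fault is that the protocol does not refer to them at the relevant places. The matter is worth correcting because it concerns subject safety and costs little; it does not bear on the efficacy analysis.

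**What to change.** The sponsor should reconcile sections 2.3, 2.7, 2.8 and 2.14 on two matters:

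1. The heat-sensation criterion should address the neutral pad site as well as the treatment area, so that eligibility matches the site where section 2.14 relies on the subject's sensation.
2. Recording of pad-site adverse events after TempSure treatment should not depend solely on the subject reporting heat.

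The clinical content of both is for the sponsor and investigators to settle, after checking what the Operator Manual and Clinical Reference Guide already require. If those documents cover the point, a cross-reference may be enough.

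The cost is a phrase in the eligibility text, an aligned sentence in the procedures and one added case report form line. The downside is that an occasional subject is not enrolled. Sample size and analysis are unchanged.

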2.12 Schedule of Visits and Procedures

	Visit #1*	Visit #2 - 5	Treatment Visit*** (Optional)	Call (Optional)	Visit #6	Visit #7
Procedure	Screening and Pretreatment Procedures	Treatment Visits 1-4 (1 - 2 weeks apart)	Treatment Visit #5 (2 - 3 weeks post last treatment)	Phone Call 1 Week Post Each Tx (1-7 Days)	Follow Up 4 Weeks Post Last Tx (+/- 1 Week)	Follow Up 12 Weeks Post Last Tx (+/- 1 Week)
Medical History	X					
Pregnancy Verification**	X	X	X			
Informed Consent	X					
Photographs	X	X	X		X	X
FWSS	X				X	X
Subject Pre-Treatment 1 Questionnaire		X				
Treatment		X	X			
Treatment Discomfort/ Pain Evaluation		X	X			
Subject Post Treatment 1 Questionnaire		X				
PGAIS					X	X
SGAIS					X	X
Subject Follow Up Questionnaire					X	X
Adverse Events Assessment	X	X	X	X	X	X

*Screening and Pretreatment Procedures may occur at the same time as the first Treatment Visit.

**Pregnancy verification required before each treatment only for women of childbearing potential.

***Group B only

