6.0 LABELING

Sample labeling will follow FDA regulations and the sponsor standard operating procedure. If applicable, the TempSure® device label will include, (in accordance with 801.1):

Statement: "CAUTION--Investigational device. Limited by Federal (or United States) law to investigational use."

Additionally, the label or other labeling will describe all relevant contraindications, hazards, adverse effects, interfering substances or devices, warnings, and precautions.

Directions for use are contained in the TempSure® Operator's Manual

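### Section 2.3 does not exclude pacemaker, ICD or CRT subjects by name, and its turn-off instruction has no cardiac exception and no prior cardiologist approval

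*Combined protocol and SAP*

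**What the plan says.** Section 2.3 deals with implanted electronics only under Cautionary Criteria, in three consecutive items.

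- A general bullet: "The subject has any embedded electronic device that gives or receives a signal, the device should be turned off or removed prior to treatment".
- A bullet for pacemakers and ICDs, under which the subject's "cardiologist must be consulted prior to treatment".
- A note: "This device has not been tested on patients implanted with electronic devices that receive or emit signals". Its examples are pacemakers, ICDs and CRT devices.

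Neither the general Exclusion Criteria nor the Icon-only exclusions name any of these implants. Two broader criteria could still keep such a subject out: the inclusion criterion "A healthy male or female 18 years of age or older", and the exclusion for a condition or situation that "in the investigators opinion may put the subject at significant risk".

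On timing, the footnote to section 2.12 states: "Screening and Pretreatment Procedures may occur at the same time as the first Treatment Visit". On other sources of rules, section 6.0 states that "the label or other labeling will describe all relevant contraindications, hazards, adverse effects, interfering substances or devices, warnings, and precautions".

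**The concern.** A subject with a cardiac implant is not barred by any named criterion, and the cautionary bullets read as directions for treating such a subject. The general bullet tells the site that the implant should be off or out. For a cardiac device, switching it off is itself a hazard, apart from any interference from the radiofrequency energy. Section 4.0 describes the TempSure handpiece output as monopolar, and section 2.7 places a neutral pad on the back. Section 3.3 adds that one handpiece in the study is not yet FDA-cleared.

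The potential harm to an affected subject is serious, while the treatment is elective and cosmetic. The wrinkle objective does not need these subjects. As written, their protection depends on how each investigator at 3 centers reads and combines the bullets.

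**Working it through.** The plan states no figure on this point, so the check is a comparison of texts plus some simple counts.

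**1. Exclusion by name.** The general exclusions cover pregnancy and breastfeeding, damaged or infected skin, anesthetic agents, heat insensitivity, and the investigator-judgment clause. The Icon-only exclusions cover systemic steroids, impaired healing, light-induced seizures, photosensitivity, abnormal scarring and prior radiation. Neither list contains a pacemaker, ICD or CRT device.

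**2. The turn-off bullet.** It applies to any embedded device that gives or receives a signal, and the note's own examples of such devices are cardiac. The bullet contains no exception and no approval step.

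**3. The cardiologist bullet.** It adds a mandatory consultation, with three limits:
- consultation is required, approval is not;
- it must precede treatment, but nothing says it must precede deactivation;
- the note lists 3 device types and this bullet names 2, so 3 − 2 = 1 type (CRT) is not expressly covered.

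**4. Comparison within the same section.** For blood thinners and anticoagulants before Icon treatment, section 2.3 makes stopping conditional: "The subject should discontinue the use of these medications if determined to be safe to do so by their prescribing physician". It then repeats the need for that physician's approval and sets a lead time of at least 2 weeks. The cardiac implant rule has neither an approval condition nor a lead time.

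**5. Process steps.** Screening and first treatment may share a visit, so the minimum gap is 0 days and no interval is reserved for a consultation. Section 2.4 speaks of verifying inclusion and exclusion criteria and does not mention the cautionary ones. The pre-treatment, treatment and post-treatment steps in sections 2.6 to 2.8 contain no consultation, deactivation or reactivation step. Nothing in the available text says who turns a device back on, or when.

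**6. Exposure per affected subject** (TempSure treatments, from section 2.1):
- Group A: up to 4, so 1 to 4 for anyone treated.
- Group B, full course: 2 TempSure-only + 2 combined = 4; with the optional fifth visit, 4 + 0 or 4 + 1 = 4 to 5. A subject who stops early has fewer.
- Overall: 1 to 5 occasions on which the turn-off bullet applies.

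The number of affected subjects is not given. It can be 0, and enrollment is capped at 50.

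**The case against.** The strongest reply is that the bullets should be read together. The turn-off bullet is general and says the device should be off; the pacemaker and ICD bullet is specific and says the cardiologist must be consulted. On that reading no such subject is treated without cardiology input, and same-day screening does not weaken the rule, because an unconsulted subject simply cannot be treated that day. This stands as far as it goes: cardiology input is required for pacemakers and ICDs, and the 0-day gap is only a supporting point. But consulting is not obtaining agreement, and the order relative to deactivation stays open.

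A sensible investigator might also apply the cardiologist rule to CRT, since the note sits directly beneath it. That is likely, but the note lists CRT separately, and a safety rule should not depend on inference.

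The health criterion, the risk exclusion and the choice of experienced investigators (section 3.2) are real safeguards. They rest on judgment, however, and the meaning of healthy is not defined. The explicit bullets point the other way by describing how to proceed.

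The protocol also places other unstudied conditions, such as diabetes and autoimmune disease, among its cautions, and its herpes caution is worded more weakly than the cardiac one. Sections 2.6 to 2.8 do not restate those physician contacts either, so the missing step there is weak evidence on its own. What sets this case apart is that the bullet says a possibly life-supporting device should be switched off or removed.

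Finally, the Operator Manual and Clinical Reference Guide were not available and may contain a contraindication. That limits the claim to the protocol text. If the manual is stricter, the protocol should be brought into line with it.

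**Conclusion.** The concern holds. Pacemaker, ICD and CRT subjects are not excluded by name, although the protocol itself says the device is untested in them. The turn-off bullet has no cardiac exception. The adjoining consultation rule covers 2 of the 3 named device types and does not require approval or precede deactivation.

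This is a subject-safety matter that the sponsor should correct. It does not touch the endpoint, sample size or analysis methods. Frequency is unknown and may be zero; an affected subject would meet the instruction 1 to 5 times. Confidence is high for the wording of the protocol. Whether a gap exists in practice also depends on attachments not seen.

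**What to change.** Add pacemakers, ICDs and CRT devices by name to the Exclusion Criteria and delete the pacemaker and ICD bullet, which is then unnecessary. Keep the turn-off bullet for non-cardiac embedded devices only, with deactivation allowed only on the approval of the physician who manages the device.

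If the sponsor wants to keep cardiac-device subjects eligible, replace the current bullets for them with a single rule. It should name all three types, require documented cardiologist approval before any deactivation or treatment, and state who turns the device back on and when.

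The cost is a short eligibility amendment with IRB approval. The only downside of exclusion is losing any otherwise eligible subjects with these implants; the documents do not give that number, and it may be zero.
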